Retrospective Clinical Study on the Effects of the Longevity Diet and Fasting-Mimicking Diet on Body Composition, Age-Related Disease Risk Factors, and Aging Markers.

1. Introduction

Aging is often accompanied by numerous chronic degenerative conditions that compromise the quality of life and lead to dependency. However, a favorable interaction between genetic and environmental factors could lead to a significantly higher life expectancy, free from conditions that significantly compromise both the quality and duration of life, highlighting that increased longevity is not necessarily accompanied by one or more pathological conditions.

It is widely accepted that the quality and quantity of nutrition are essential factors in maintaining health and preventing diseases (1-3). Making healthy and conscious dietary choices can indeed alter the course of life in terms of both duration and health.

Numerous epidemiological studies have demonstrated the critical role of a proper dietary regimen in the risk of developing age-related diseases (4). Furthermore, recent studies have highlighted how short periods of extreme calorie reduction with adequate nutrient intake (5 days, fasting-mimicking diet, FMD) can impact metabolism, producing numerous beneficial effects in both healthy individuals and those with chronic degenerative conditions such as cancer, cardiovascular diseases, diabetes, and autoimmune diseases (5-7). Theories about senescence usually focus on the aging process and not on the ability of organisms to stay young. The longevity diet (8) proposed in this study is intended to be effective in achieving the goal of extending youth for as long as possible, optimizing protection, regeneration, and rejuvenation while minimizing diseases. It is based on five pillars that support the scientific evidence of the program: basic research, epidemiology, clinical studies, centenarian studies, and complex systems studies. Essentially, the longevity diet incorporates the dietary tradition of healthy centenarians, characterized by simplicity and products typical of their region of origin.

This type of diet generally consists of three isocaloric meals and one snack (for normal-weight individuals) or slightly hypocaloric meals (in the case of overweight or obesity). The diet consists of 50-60% of calories from complex carbohydrates, 30-35% of calories from mostly unsaturated fats, and 10-11% of calories from proteins, primarily from plant sources and fish, and occasionally from eggs, dairy, and meat, especially for those over 65. The diet is formulated to provide all necessary nutrients, including vitamins and minerals.

The fasting-mimicking diet is a dietary intervention in which normal food is replaced with a standardized, highly hypocaloric vegan diet for a limited period of 5 consecutive days. This diet is designed to stimulate the same processes normally activated during fasting while minimizing the side effects of total food deprivation.

This retrospective clinical study aims to investigate the two different approaches: the longevity diet and the fasting-mimicking diet, to assess both their feasibility and effectiveness when used individually or in combination.

1.1 Background and Hypotheses

The Italian population has moved away from the traditional Mediterranean diet and now predominantly follows a Western-style diet that is hypercaloric, rich in saturated fats, animal protein, and sugars (12). We hypothesize that a return to the original Mediterranean diet with modifications based on the scientific evidence of recent decades (longevity diet), and/or short periods of fasting-mimicking diet (5 days), can improve the overall health conditions of the population (9-11).

2. Objectives and Purpose of the Study

Primary Objective: To evaluate whether the longevity diet and the fasting-mimicking diet, either individually or in combination, can reduce the percentage of body fat in a cohort of subjects stratified by gender, age, body mass index, and defined physio-pathological states.

Secondary Objectives: To assess whether the longevity diet and the fasting-mimicking diet, either individually or in combination, can positively influence parameters related to the general health status of the analyzed sample, including (i) percentage of lean mass, (ii) phase angle as an indirect indicator of muscle function and cellular integrity, (iii) waist and hip circumference, (iv) total cholesterol, HDL, and LDL.

This is a retrospective, observational, single-center study to evaluate the effect of specific nutritional interventions (fasting-mimicking diet (FMD) and longevity diet (LD)) on reducing body fat. To achieve this, retrospective data from bioimpedance, anthropometric, and clinical analyses of subjects who underwent at least one of the two nutritional interventions (individually or in combination) at the Valter Longo Foundation in Milan from 2019 to 2022 will be analyzed. In particular, information from subjects who underwent at least two nutritional visits with bioimpedance analysis with a gap of at least 3 months between them will be considered. The subjects will be characterized based on (i) the type of nutritional intervention (FMD only, LD only, or combinations of LD and FMD); (ii) the duration of the nutritional intervention (short, medium, or long); (iii) the degree of obesity (normal weight, overweight, and obese); and (iv) physio-pathological status.

4. Data Collection and Analysis

Data will be collected retrospectively from the electronic medical records of the Valter Longo Foundation. Bioimpedance analysis, anthropometric measurements, and clinical parameters including lipid profiles will be used to assess changes in body composition, body fat percentage, lean mass percentage, phase angle, waist circumference, hip circumference, and blood lipid levels.

5. Statistical Analysis

Statistical analyses will be performed using appropriate statistical software packages. Descriptive statistics will be used to summarize baseline characteristics, and paired t-tests or non-parametric equivalents will be used to compare pre- and post-intervention measurements. Analysis of variance (ANOVA) will be used to compare outcomes across different subgroups based on type of intervention, duration, degree of obesity, and physio-pathological status. Correlation analyses may also be performed to explore associations between changes in body composition and other variables. A p-value of less than 0.05 will be considered statistically significant.

6. Ethical Considerations

This study will be conducted in accordance with ethical principles and regulations governing clinical research. All data will be de-identified and handled in compliance with data protection regulations. Informed consent will be obtained from all subjects included in the study.

7. Conclusion

This retrospective clinical study aims to investigate the effects of the longevity diet and the fasting-mimicking diet, either individually or in combination, on body composition, age-related disease risk factors, and aging markers. The study will provide valuable insights into the potential benefits of these dietary interventions in promoting health and longevity, which could have significant implications for public health and wellness.

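### Lean mass is listed only as an undefined percentage: a rise does not by itself show a lean-mass benefit and may only mirror the body-fat result

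*Combined protocol and SAP*

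**What the plan says.** Section 2 (Objectives and Purpose of the Study) makes fat percentage the primary outcome: the question is whether the diets, alone or combined, "can reduce the percentage of body fat in a cohort of subjects". The secondary objective asks whether they "can positively influence parameters related to the general health status of the analyzed sample", and its list opens with "i) percentage of lean mass, (ii) phase angle as an indirect indicator of muscle function and cellular integrity".

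Eligible subjects have "at least two nutritional visits with bioimpedance analysis with a gap of at least 3 months between them". Section 4 lists what will be assessed: "changes in body composition, body fat percentage, lean mass percentage, phase angle, waist circumference, hip circumference, and blood lipid levels". Lean mass is therefore named twice, each time as a percentage. No section names the compartment, the bioimpedance device or the equation. Lean mass in kg, fat mass in kg and body weight are not named as outcomes.

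In Section 5, "paired t-tests or non-parametric equivalents will be used to compare pre- and post-intervention measurements", and "Analysis of variance (ANOVA) will be used to compare outcomes across different subgroups". The significance level is 0.05, with sidedness not stated.

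**The concern.** Two separate problems follow.

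- **Redundancy.** Fat % and lean % come from the same bioimpedance analysis. If lean mass is everything that is not fat, the two percentages sum to 100 and the secondary outcome contains no new information. Two significant results would look like agreement between outcomes when they are one result reported twice.
- **Interpretation.** A percentage has body weight in its denominator. When weight falls, lean % can rise because fat fell faster than lean, even though lean tissue was lost. Under the plan as written, that rise would count as a positive influence.

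The second problem arises in subjects who lose weight. Section 1 makes weight loss plausible: the longevity diet is described as "three isocaloric meals and one snack (for normal-weight individuals) or slightly hypocaloric meals (in the case of overweight or obesity"), and the fasting-mimicking diet restricts calories severely for five days. Section 2 includes overweight and obese subjects and all three intervention patterns. The documents do not say whether weight lost on the fasting-mimicking diet persists to visits at least 3 months apart.

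**Working it through.** The plan states no weights, fat percentages, effect sizes or sample size, so there is no figure of its own to reproduce. The algebra below needs no trial data. All body weights, fat percentages and losses are illustrative assumptions.

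**1. Mirror of the primary.** Let W be weight, F fat mass and L lean mass, with W = F + L. Then lean % = 100 L/W = 100 - fat %, so each subject's change in lean % is minus the change in fat %. Reversing the sign leaves the two-sided p-value of a paired t-test or signed-rank test unchanged, and leaves the ANOVA F statistic unchanged. In a simulation of 200 subjects with assumed inputs (mean weight 80 kg, mean fat 32%, mean loss 4 kg, 25% of it lean), the paired t was -16.43 for fat % and +16.43 for lean %, while mean lean mass fell by 1.14 kg.

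**2. When lean % rises during weight loss.** Let D > 0 be the weight lost and s the lean share of that loss. Lean % rises if (L - sD)/(W - D) > L/W. Cross-multiplying gives LD > sWD, that is, s < L/W. The break-even share is the baseline lean fraction. For any s above 0 and below L/W, lean % rises while lean kg falls.

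**3. One rise in lean %, different changes in kg.** New lean kg = new lean fraction × (W - D).

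| Baseline | Lean % | Weight lost | New lean kg | Change |
|---|---|---|---|---|
| 80 kg, 30% fat (L = 56) | 70.0 to 72.0 | 0 | 0.72 × 80 = 57.6 | +1.6 kg |
| same | same | 2.2 kg (80 - 56/0.72) | 56.0 | 0.0 kg |
| same | same | 3 kg | 0.72 × 77 = 55.4 | -0.6 kg |
| same | same | 5 kg | 0.72 × 75 = 54.0 | -2.0 kg |
| 95 kg, 40% fat (L = 57) | 60.0 to 62.0 | 0 | 0.62 × 95 = 58.9 | +1.9 kg |
| same | same | 3.1 kg (95 - 57/0.62) | 57.0 | 0.0 kg |
| same | same | 6 kg | 0.62 × 89 = 55.2 | -1.8 kg |

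**4. One weight loss, different lean shares.** 80 kg, 30% fat, 5 kg lost: lean % after = 100 × (56 - 5s)/75.

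| Lean share s | Lean % after | Change in lean % | Change in lean kg |
|---|---|---|---|
| 0 | 74.7 | +4.7 points | 0.0 |
| 0.2 | 73.3 | +3.3 points | -1.0 |
| 0.6 | 70.7 | +0.7 points | -3.0 |
| 0.7 (break-even) | 70.0 | 0.0 points | -3.5 |
| 0.8 | 69.3 | -0.7 points | -4.0 |

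**5. Narrower definitions.** Excluding an assumed 3 kg of bone in the s = 0.2 case, lean % goes from 53/80 = 66.25 to 52/75 = 69.33, a rise of 3.1 points against a fall of 3.3 in fat %: a near-mirror. In the simulation, bone-free lean % correlated -0.999 with fat % when no separate estimation error was added, and -0.94 to -0.67 with an assumed added error SD of 0.5 to 2.0 kg. How redundant the outcome is therefore depends on the definition that the plan omits.

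**The case against.** The plan never claims that lean mass will be preserved or gained. It asks about a percentage, and lean % is a legitimate description of composition. The general reference to body composition in Section 4 leaves room for kg measures, and phase angle is a separate muscle-related outcome. The exact mirror needs the fat-free-mass definition, and the kg discrepancy needs weight loss that lasts to the later visit. The longevity diet is isocaloric in normal-weight subjects, and every magnitude above is assumed. The remedy also adds two outcomes to a plan that states no multiplicity adjustment, and no separate case is made for fat mass in kg.

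Much of this limits the reach of the point. At stable weight, lean % and lean kg move together, and nothing in the documents shows how many subjects lose weight or how much. Fat kg is only a by-product of the same split, and the argument rests on lean kg. The added outcomes are a real, small cost.

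The objection does not remove the problem. Leaving room for kg measures does not commit to any. Phase angle is described as indirect and does not measure the amount of lean tissue. A secondary objective framed as a positive influence on health invites a rise in lean % to be read as a benefit to lean tissue, and nothing in the plan guards against that. The identity and the break-even rule hold whatever the trial's data.

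**Conclusion.** The concern holds. Lean mass is undefined and committed to only as a percentage. Under the fat-free-mass reading it duplicates the primary exactly; bone-free lean mass gives a near-duplicate, and a separately estimated muscle mass a looser link. In subjects who lose weight, a rise in lean % is compatible with a gain, no change or a loss of lean kg. In the assumed 80 kg case, a rise of 2.0 points spans +1.6 to -2.0 kg over losses of 0 to 5 kg.

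Confidence is high for the algebra and for the missing definition. The size and frequency of the discrepancy in this cohort cannot be judged without weight data. The primary inference stands, so this is a cheap improvement to one secondary outcome and does not threaten the study's main result.

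**What to change.** - In Section 2 or 4, state which bioimpedance output lean mass is: fat-free mass, bone-free lean mass or muscle mass.
- Confirm that weight is recorded at both visits. Then add two secondary outcomes, each reported as a mean change with a 95% confidence interval: fat mass in kg (weight × fat %/100) and lean (fat-free) mass in kg (weight minus fat mass).
- Base any statement that lean mass was preserved or improved on the kg change.
- Keep lean % as listed. If it is 100 minus fat %, or nearly so, report it as the complement of the primary and not as independent confirmation. If it is a separately estimated muscle mass, it remains an ordinary secondary outcome, read alongside the kg change.

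The cost is protocol and SAP wording plus two derived variables. Weight at both visits is implied by the BMI stratification and by bioimpedance but is not stated. The secondary list grows by two with nothing removed; Section 5 states no multiplicity adjustment, so the additions are best presented as estimates with intervals. The lean-mass result may look less favourable than the percentage alone. Fixing this before analysis avoids choosing the measure after seeing the results.

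### The before-after lipid comparisons take no account of lipid-lowering treatment started, stopped or changed between readings, so an apparent diet effect could be inflated or masked

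*Combined protocol and SAP*

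**What the plan says.** Section 2 (Objectives and Purpose of the Study) makes the lipids a secondary outcome, "iv) total cholesterol, HDL, and LDL". It asks whether the diets, alone or combined, "can positively influence parameters related to the general health status of the analyzed sample".

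The design paragraph that follows the objectives takes its data from "subjects who underwent at least one of the two nutritional interventions (individually or in combination"), so everyone in the cohort was exposed to a diet. Records run from 2019 to 2022. Subjects with "at least two nutritional visits with bioimpedance analysis with a gap of at least 3 months between them will be considered"; no maximum gap is given and there is no condition on medication. Subjects are characterised by type and duration of intervention, and by "iii) the degree of obesity (normal weight, overweight, and obese); and (iv) physio-pathological status". The primary objective likewise speaks of "defined physio-pathological states", without listing them.

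Section 4 says: "Data will be collected retrospectively from the electronic medical records". It then says: "Bioimpedance analysis, anthropometric measurements, and clinical parameters including lipid profiles will be used to assess changes in body composition". No medication is named.

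Section 5 compares values before and after with a paired t-test or a rank-based counterpart, compares subgroups by ANOVA, allows optional correlation analyses, and sets significance at p below 0.05.

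**The concern.** Lipid-lowering drugs exist to change exactly what is measured here, and the cohort is characterised in part by pathological status. A subject whose drug treatment changes between two readings contributes a paired difference that mixes drug and diet. The paired test cannot separate the two, and there is no untreated group in which a drug effect would show up on its own.

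Nothing else in the plan covers this. Physio-pathological status groups subjects; it does not record what happened to their treatment between readings, and grouping by it leaves a within-person drug effect in the difference. ANOVA across diet groups would cancel the effect only if treatment changes were equally common and equally strong in each group, which the plan neither states nor checks.

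At stake are three of the eight named outcomes (body fat, lean mass, phase angle, waist, hip and three lipids), all three of them secondary. A lipid change reported under the causal wording of the objective could be partly a drug effect, or a real diet effect could be hidden.

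**Working it through.** **No plan figure to reproduce.** The documents give no sample size, standard deviation, effect size, lipid level or frequency of drug use. Every number below except the 0.05 level is an assumption made for illustration, and only LDL is illustrated.

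**1. Text check.** Eligibility, subject characterisation, data collection and analysis were read for any handling of medication. It does not appear as an exclusion, an extracted variable, a stratum, a covariate or a sensitivity analysis.

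**2. Relative bias.** Let f be the net share of subjects who start a drug (starts minus stops) and r the relative fall in LDL that it produces. With no diet effect, and starters having about the same initial LDL as the rest, the fall in mean LDL is f × r.
- Low: 3% × 20% = 0.6%
- Middle: 10% × 30% = 3%
- High: 20% × 40% = 8%

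**3. Effect on the paired test.** Let D be the drug effect in mg/dL and SD the standard deviation of LDL change without it. With no diet effect:
- mean change = −f × D
- variance of change = SD² + f(1 − f)D²
- chance of p < 0.05 = 1 − Φ(1.96 − d) + Φ(−1.96 − d), where d = fD ÷ (standard error) and the test is taken as two-sided, since the plan does not say.

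Middle case, SD 30, D 50, f 5%, n 200: mean change −0.05 × 50 = −2.5 mg/dL; variance 900 + 0.05 × 0.95 × 2,500 = 1,018.75; standard error √(1,018.75 ÷ 200) ≈ 2.26; d ≈ 1.11; chance of a significant result ≈ 19.8%.

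| SD | D | f | Mean change (mg/dL) | n = 100 | n = 200 | n = 500 |
|---|---|---|---|---|---|---|
| 30 | 30 | 2% | −0.6 | 5.5% | 5.9% | 7.3% |
| 30 | 50 | 5% | −2.5 | 12.3% | 19.8% | 41.8% |
| 20 | 50 | 10% | −5.0 | 51.6% | 80.7% | 99.4% |

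With f = 0 the formula returns 5.0%, as it should. The bias does not shrink as n grows, so a larger cohort makes a spurious finding more likely.

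**4. The other direction.** If stops exceed starts, f is negative and the sign reverses. With 5% net stops and a 50 mg/dL rise on stopping, the mean change is +2.5 mg/dL, which would cancel a true diet benefit of that size.

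**5. What happens if subjects with a change are simply dropped.** Suppose no diet effect, SD 25 mg/dL, and that the 10% who start a drug are excluded. If starting has correlation ρ with a rise in underlying LDL, the remaining 90% have mean change −ρ × 25 × 0.1755 ÷ 0.9 = −4.875ρ, where 0.1755 is the normal density at the 90th percentile.
- ρ = 0.3: −1.5 mg/dL
- ρ = 1.0: −4.9 mg/dL

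This is similar in size to the bias in step 3 (−0.6 to −5.0 mg/dL) and favours the diet. Restriction alone is therefore not a safe remedy.

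**The case against.** The strongest reply is that this is one instance of a general weakness. Any uncontrolled before-after comparison is open to other treatments, regression to the mean and time trends, and calling the lipid results changes over time would cover all of them. That is fair, and the fix uses it as the fallback. The drug issue still deserves its own line because it may be partly checkable in records already being read.

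Second, materiality is not shown. The size rests wholly on assumed figures, and the chance of a spurious result runs from practically nominal to near certain. This stands and limits the weight of the point.

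Third, the data may not be there. Eligibility rests on two bioimpedance visits, not two dated lipid readings. The records belong to the foundation where the nutritional visits took place and may miss treatment changed elsewhere, and a blank field does not separate no change from not asked. This also stands. It is a reason to limit the lipid claim, not to leave the matter out.

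Fourth, the document is short and its list of clinical parameters is not closed, so the absence of medication data is inferred from silence. A reader might conclude that medication is not recorded or will not be extracted; the text shows only that the plan does not mention it or say how it would be used.

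A reader might also infer that subjects were followed for several years in ordinary care, or that the plan credits the whole lipid change to diet. The text supports neither. It gives a minimum gap, a 2019 to 2022 window and undefined duration classes, and it calls the study observational even though the objective is worded causally.

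**Conclusion.** The point holds in a limited form. Following the plan as written can give a biased lipid result, because the paired comparison has no untreated group and takes no account of treatment changes. The direction is unknown: net starts inflate the apparent diet effect and net stops mask it. The size is unknown too; the 0.6% to 8% fall in mean LDL depends on the assumed 3% to 20% net starters and 20% to 40% drug effect, and could be negligible in this cohort. Nothing has been quantified for HDL or total cholesterol.

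Two stronger readings are tempting. One is that a drug effect will be reported as a diet benefit; the documents say nothing on how often treatment changed or which way. The other is that subjects without a treatment change should form the main analysis; a treatment change comes after the diet begins and may depend on lipid response, so that choice can introduce its own bias in favour of the diet.

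The primary outcome, body fat percentage, is not touched by this point. It is a minor improvement, held with low confidence.

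**What to change.** - Where recorded, extract lipid-lowering treatment at the time of each lipid reading.
- Report the number of starts, stops and other changes by diet group.
- Present the paired lipid results in all subjects. Beside them, as a sensitivity analysis, give the results in subjects with no recorded change. Do not make the restricted set the main analysis.
- Where medication is not recorded, report how many subjects are affected and describe the lipid results as changes over time, not as diet effects. Do not count a blank field as no change.

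The cost is some extra extraction from records already being read, fields that may prove incomplete, and a smaller and possibly selected subset in the sensitivity analysis. The fallback wording needs no new data. The change concerns only extraction, analysis and reporting.

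### The objectives ask what the diets do to body fat, but the only planned test of a reduction is a before–after comparison in people who all followed a diet

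*Combined protocol and SAP*

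**What the plan says.** **The question.** The title and Section 7 speak of the diets' effects, and the last paragraph of the Introduction speaks of their effectiveness. In Section 2 the primary objective is whether the diets, alone or together, "can reduce the percentage of body fat in a cohort of subjects stratified by gender, age, body mass index, and defined physio-pathological states". The secondary objectives ask whether they "can positively influence parameters related to the general health status of the analyzed sample". The design paragraph that closes Section 2 calls the study retrospective and observational, and in the same sentence gives its purpose as "to evaluate the effect of specific nutritional interventions (fasting-mimicking diet (FMD) and longevity diet (LD)) on reducing body fat".

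**The subjects.** The same paragraph draws on records of "subjects who underwent at least one of the two nutritional interventions (individually or in combination", and restricts them to "subjects who underwent at least two nutritional visits with bioimpedance analysis with a gap of at least 3 months between them". The exposure groups are fasting-mimicking diet only, longevity diet only, and combinations. There is no group without a diet.

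**The analysis.** Section 5 plans descriptive statistics, and then "paired t-tests or non-parametric equivalents will be used to compare pre- and post-intervention measurements". ANOVA is to "compare outcomes across different subgroups based on type of intervention, duration, degree of obesity, and physio-pathological status". Correlations are optional, and significance is set at p<0.05. Section 5 names no covariates, no comparator and no limit on what a significant result may be taken to mean.

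**The concern.** A question about whether a diet reduces body fat compares what happened on the diet with what would have happened without it. Nothing in the plan estimates the second quantity. A paired test puts each person's own baseline in its place, which amounts to assuming that nothing else would have changed over 3 months or more.

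Other causes of change are easy to name:

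- **Selective return.** This is built into eligibility, because people who did not come back are not analysed.
- **Concurrent changes.** Records run from 2019 to 2022 and no maximum gap between visits is set, so exercise, medication, other advice and calendar effects can all contribute.
- **Clinic contact.** Attending a nutrition clinic may change behaviour apart from the specific diet.
- **Regression to the mean.** This is possible if people sought help when their body fat was high.

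The stake is the primary conclusion. A significant paired test could credit the diets with change they did not produce. A null result could hide a real effect offset by other causes. Section 7 already looks ahead to public health implications.

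**Working it through.** **Step 1. Does any planned analysis contrast diet with no diet?**

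| Planned analysis (Section 5) | Contrast | Answers whether the diets reduce body fat? |
|---|---|---|
| Paired t-test or non-parametric equivalent | After v. before, all on a diet | No: net change from any cause |
| ANOVA by diet type | Treated v. treated, not randomised | No: whether diet groups differ |
| ANOVA by duration | Treated v. treated | No: can be confounded with follow-up time and adherence |
| ANOVA by obesity or health status | Treated v. treated | No |
| Optional correlations | Within treated subjects | No |

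The paired comparison is therefore the only planned test of a reduction. Gender and age are stratifiers in the primary objective but do not appear in Section 5.

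**Step 2. What does the paired test respond to?** The plan has no power calculation to reproduce. It gives no sample size, SD or effect size and does not say whether tests are one- or two-sided. All inputs below are assumptions, with two-sided 0.05. The figures show how the test behaves, not how large any bias is.

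For paired differences with mean m and SD s, the t statistic is noncentral t with n − 1 degrees of freedom and noncentrality m√n/s. Set the diet effect to zero and let m be the non-diet change, in percentage points of body fat. For m = 0.5, s = 3 and n = 200, the noncentrality is 0.5 × √200 / 3 = 2.36 and the test rejects in 65.0% of studies.

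Chance of p<0.05 in either direction with zero diet effect (SD 3, with the range over SD 4 to SD 2 in brackets):

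| Non-diet change | n = 100 | n = 200 | n = 500 |
|---|---|---|---|
| 0 | 5% | 5% | 5% |
| 0.1 | 6% (6–8) | 8% (6–11) | 12% (9–20) |
| 0.25 | 13% (9.5–24) | 22% (14–42) | 46% (29–80) |
| 0.5 | 38% (24–70) | 65% (42–94) | 96% (80 to nearly 100) |

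The rate rises with n: a larger sample makes false attribution more likely.

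**Step 3. The other direction.** Assume a true diet reduction of 0.5 points and SD 3. The chance of a significant reduction is 38%, 65% and 96% at n = 100, 200 and 500. With an opposing non-diet gain of 0.25 points, the net change is 0.5 − 0.25 = 0.25, and the chance falls to 13%, 22% and 46%.

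**Step 4. Would the ANOVA reveal the problem?** A three-group ANOVA of change was simulated (10,000 runs per setting) with a shared non-diet change of 0 to 0.3 SD and no diet effect. It rejected in about 5% of runs in every setting. A shared non-diet change is invisible to it.

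**Step 5. Would a comparator help?** Under the same shared changes, a two-group test of change against an otherwise comparable concurrent no-diet group rejected in 4.5% to 5.3% of runs. The missing comparator is therefore the source of the problem.

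**The case against.** The best reply is that the plan does not disguise its design. It calls itself retrospective and observational, Section 7 speaks only of potential benefits, and paired before–after analysis of clinic records is a legitimate descriptive method. Section 5 never says that a significant paired test answers the primary objective, and since the main remedy is wording, this could be treated as a lesser matter.

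Part of this stands. The paired test is valid for within-person change and should be kept. The link from test to objective is an inference, though no other planned test could serve. The labels do not settle the matter, because they restrict no conclusion and the sentence that says observational also sets out to evaluate an effect.

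Three narrower points:

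- **The ANOVA may be multi-factor.** The text does not say. If it is, diet type would be adjusted for obesity and health status, but still not for baseline body fat, age, gender or time between visits.
- **Regression to the mean is not documented.** There is no body-fat or BMI entry threshold, and normal-weight subjects are included. It is a possible cause only; the required return visit is the documented selection mechanism.
- **The table counts significance in both directions,** whereas false credit concerns reductions only. This matters only in the 0.1-point row, by about one point. At SD 3 and n = 100, reductions alone give 5.2% (against 2.5% with no change), compared with 6.3% (against 5%).

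**Conclusion.** The concern holds. The primary question is causal, every analysed subject was on a diet, and the only test of a reduction measures net change. This follows from the text and needs no numerical assumption. It must be corrected because it governs what the primary result may be said to show, and no later analysis of treated-only records can supply the missing contrast.

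The size of any bias is unknown. The percentages rest wholly on assumed sample sizes (100 to 500), SDs of change (2 to 4 points) and non-diet changes (0.1 to 0.5 points). Nothing in the documents shows that such changes occurred, or in which direction.

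**What to change.** 1. **Restate the claims.** Reword the title, the Introduction's aim, the primary and secondary objectives, the design sentence and Section 7 as change observed during follow-up in people following either diet or both. Keep the paired analysis, report mean change with a 95% CI, and state in Section 5 that the change is not attributed to the diet. If the sponsor wishes to keep the causal question, a comparator is needed, such as comparable records without either diet or repeated pre-diet measurements. The documents do not say whether these exist.

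2. **Separately, improve the between-diet comparison.** In place of the ANOVA of diet type, regress follow-up body fat on diet group, with baseline body fat, age, gender, BMI, health status and time between visits. Report differences as associations and acknowledge residual confounding. Time between visits is determined after the diet starts and may reflect who continued, so show results with and without it. This model does not supply an untreated comparator.

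3. **Minor.** No listed variable is labelled an aging marker; phase angle is the nearest. Name the variable meant or drop the term.

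The cost is rewording and one regression. It uses characteristics the plan already names and the visit dates needed to apply the 3-month rule. Eligibility does not change. The price is a more modest claim.
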